7.3 Ophthalmologic Examination

The following examinations will be performed at all time-points specified in [Section 10.2](#) “Trial Assessments”.

- Examination of the eyelids
- Examination of extra-ocular muscle movement
- Examination of the cornea
- Examination of the anterior chamber
- Examination of the pupils

- Examination of the iris
- Examination of the lens
- Examination of the vitreous body
- Examination of the retina and optic disc

7.4 Fundus Photography, Fluorescein Angiography, Fundus Autofluorescence, and Optical Coherence Tomography (SD-OCT)

Color stereoscopic fundus photographs, fluorescein angiography (FA), FAF, and spectral-domain optical coherence tomography (SD-OCT) will be performed at all time-points specified in [Section 10.2 “Trial Assessments”](#).

All color fundus photos, FAs, FAFs, and SD-OCTs that are collected at protocol-specified time points must be sent to the reading center (RC) as specified in the RC procedure manual. The RC will provide instructions for the CFP, FA, FAF, and SD-OCT procedures.

7.5 Pregnancy Tests and Birth Control

A urine pregnancy test will be performed for women of childbearing potential prior to avacincaptad pegol intravitreal administration at the visits as indicated in [Section 3, “Study Assessments”](#), and in [Section 10.2 “Trial Assessments”](#).

For patients who are women of childbearing potential, the same protocol approved highly effective contraceptive method must be used for at least one month prior to study entry and during the trial until at least 90 days following the last dose of test medication. Protocol approved highly effective contraceptive methods are:

- Hormonal contraceptives (i.e., combined oral contraceptive, patch, vaginal ring, injectable, or implant),
- Intrauterine devices or intrauterine systems,
- Vasectomy, and/or tubal ligation,
- Abstinence, defined as refraining from heterosexual intercourse during the entire period of the study and until at least 90 days following the last dose of study medication if in accordance with usual lifestyle.

If the patient is a woman of childbearing potential, she must have no plans to donate ova during the duration of the trial and for at least 90 days following the last dose of test medication.

Non-childbearing potential is defined as follows:

- A woman who has had surgical sterilization (hysterectomy, bilateral oophorectomy, or bilateral salpingectomy)
- A woman ≥ 60 years of age
- A woman ≥ 40 and < 60 years of age who fulfills at least one of the following:
 - A cessation of menses for at least 12 months and a follicle-stimulating hormone (FSH) test confirming non-childbearing potential (refer to laboratory reference ranges for confirmatory levels)
 - A cessation of menses for at least 24 months without FSH levels confirmed

Czech Republic, Poland, France, Italy: If the patient is male, he should use a condom and not donate sperm during the time of study drug exposure and for 90 days following the last exposure of study drug.

7.6 Immunogenicity

Assessments of anti-drug antibodies (ADA) will be performed at pre-dose at Month 1, Month 2, Month 4, Month 7, Month 13, and Month 18 as specified in [Section 10.2 “Trial Assessments”](#). The pre-dose sample taken at Month 1 will be considered the serum sample taken prior to dosing of avacincaptad pegol for Sham patients crossing over to avacincaptad pegol to capture a drug-free baseline.

Two serum samples of 2 mL will be collected at each timepoint specified: one for primary analysis and one as a back-up.

The Sponsor may request ad-hoc ADA sampling in the event of an adverse drug reaction.

7.7 Pharmacokinetics

The concentration of avacincaptad pegol in K₂EDTA human plasma samples will be quantified using validated electrochemiluminescence dual hybridization assay and expressed in terms of ng/mL. Plasma PK samples will be collected at pre-dose at Month 1 (baseline), Month 2, Month 4, Month 7, Month 13, and Month 18 as specified in [Section 10.2 “Trial Assessments”](#) prior to administration of avacincaptad pegol in order to evaluate the effect of ADA on the plasma concentrations of avacincaptad pegol.

8 SUBJECT POPULATION

8.1 Sample Size

Approximately 280 patients will be enrolled.

8.2 Inclusion Criteria

Male or female patients aged 50 years or greater diagnosed with GA inside and/or outside of the fovea who completed Study ISEE2008 (GATHER2) through the Month 24 visit on study treatment, regardless of whether they received treatment with avacincaptad pegol or Sham previously, refer to Section 8.2 of the ISEE2008 protocol for inclusion criteria details. Patients must provide new written informed consent for this OLE trial prior to participating and have the ability to return for all trial visits for the duration of the 18-month trial.

Information on the conduct of patients who are or are not women of childbearing potential and contraception usage in men and women is provided in [Section 7.5](#).

8.3 Exclusion Criteria

Patients will ***not be eligible for the trial*** if:

1. Patient did not complete Study ISEE2008 (GATHER2) through the Month 24 visit on study treatment (either avacincaptad pegol or Sham),
2. Any patients who had the study drug permanently withdrawn for an AE are not eligible; patients who had study drug temporarily withheld for an AE(s) or elective ocular surgery will be reviewed on case by case basis for eligibility,
3. Patient did not enroll into this OLE trial within the 90 days enrollment period.
4. Patients who are pregnant or nursing

9 TRIAL MEDICATION

9.1 Drug Supply

9.1.1 Avacincaptad pegol

Avacincaptad pegol is a PEGylated RNA aptamer consisting of a 13 kDa modified RNA aptamer that is conjugated at the 5' terminus to a ~43 kDa branched PEG moiety. The aptamer portion of avacincaptad pegol is 39 nucleotides in length and modified to a primary amine at the 5' terminus to provide a reactive site for subsequent conjugation ("PEGylation"). The nucleotide composition consists of purine ribonucleotides and modified 2'-fluoro pyrimidines and 2'-methoxy purines. The modified nucleotides minimize susceptibility to endonuclease digestion. The 3' terminus is capped with an ("inverted") 3'-3' phosphodiester linkage to a deoxythymidine nucleotide to maximize resistance to 3'-exonuclease degradation. PEGylation is employed to improve residence time in vivo. All concentrations and doses for avacincaptad pegol (1 μ M = 13 μ g/mL) are based on the mass of the aptamer, exclusive of the PEG mass.

Avacincaptad pegol drug product is formulated at a concentration of 20 mg/mL (oligonucleotide mass) in 10 mM phosphate buffered saline at pH 6.8 to 7.8 as a sterile aqueous solution and will be supplied in a sealed vial by the Sponsor. Sodium hydroxide or hydrochloric acid may have been added for pH adjustment. The product is a preservative-free clear solution and intended for intravitreal (IVT) injection only. The product should not be used if cloudy or if particles are present.

Avacincaptad pegol will be supplied in single use sterile glass vials for intravitreal injection.

Active ingredient: avacincaptad pegol

Avacincaptad pegol is formulated as: 20 mg/mL solution for injection

Excipients: Sodium Chloride, United States Pharmacopeia (USP)
Sodium Phosphate Monobasic, Monohydrate, USP
Sodium Phosphate Dibasic, Heptahydrate, USP
Sodium Hydroxide, National Formulary (NF; as needed)
Hydrochloric acid, NF (as needed)
Water for injection, USP

9.1.2 Treatment Regimen and Duration

Patients may receive monthly injections of 0.1 mL (100 µL) avacincaptad pegol 2 mg for up to 18 months (maximum 17 total doses), starting at Month 1 through Month 17. Monthly doses will be administered at least 21 days apart.

All patients will have a final follow up visit at Month 18.

Subjects will continue in the trial for up to 18 months or until one of the following occurs: the subject withdraws consent and discontinues from the trial, the subject is discontinued from the trial at the discretion of the Investigator or the Sponsor, or the trial is terminated. Refer to [Section 10.4](#) and [Section 10.510.6](#) for patient withdrawal and trial discontinuation information, respectively.

9.1.3 Administration of Study Drug

Each study medication kit contains a 5-micron filter needle, a 30 G injection needle, a 1 mL empty syringe, and a vial of avacincaptad pegol 2 mg, to be administered by IVT injection. The method for IVT administration of avacincaptad pegol is described in detail in [Appendix 17.2](#).

After administration, discard the contents inside of the carton in accordance with local regulations, complete the vial tear-off label, and place in the subject source documents for the monitor to conduct study drug reconciliation.

9.1.4 Drug Accountability

A drug accountability log will be provided by the Sponsor and must be maintained by the clinical site. The drug accountability log must be kept current and must contain the date and drug units [lot number, subject number, date of dispensation and initials of the dispenser].

At the end of the trial or when indicated by the Sponsor, all unused study medication should be destroyed locally by the study site. Where local laws or site procedures do not permit local site destruction the Sponsor will provide instructions for the return of unused medication to a local depot. Sites that destroy study medication locally must be able to produce a certificate of destruction upon request of the Sponsor.

9.1.5 Storage

The Investigator, or an approved representative (e.g., pharmacist), will ensure that all study drugs are stored in a secured area, under recommended storage conditions and in accordance with applicable regulatory requirements. All study medication kits should be stored at all times under refrigeration (2 to 8°C; 36 to 46°F) as per the study medication label; do not freeze. All vials should be protected from light and stored in the originally provided carton or clinical kit,

until the time of use. Any deviations in storage temperature should be reported to the Sponsor prior to administering the drug to study subject. The Sponsor will determine if the study drug remains stable and can be administered to subjects.

9.2 Previous or Concomitant Therapy

Only patients completing the Month 24 visit of Study ISEE2008 are eligible for this OLE trial, patients who discontinued for any reason are not eligible. Therefore, patients enrolled will have had no previous treatment for GA except for previous treatment with avacincaptad pegol 2 mg in Study ISEE2008.

If subject has a history of wet AMD or if wet AMD were to develop during the trial, in either the study eye (SE) or the fellow eye (FE), please refer to [Section 10.3](#) for guidance on the use of concomitant treatment.

9.2.1 Prohibited Medication

Use of medications listed in the below table are not permitted after start of study intervention.

Prohibited Medication

Medication	Recommended Action
Study Eye Anti-VEGF therapy (licensed, unlicensed or investigational) other than Eylea, Lucentis, or Vabysmo; use of other biologics Other investigational treatment	Discontinue study treatment Discontinue study treatment
Fellow Eye Anti-VEGF therapy (licensed, unlicensed or investigational) other than Eylea, Lucentis, or Vabysmo Other investigational treatment	None Discontinue study treatment
Systemic Anti-complement therapy Any new systemic medication known to be toxic to the lens, retina, or optic nerve (including, but not limited to hydroxychloroquine, tamoxifen) Any investigational drug, biologic or device (with the exception of over-the-counter vitamins, supplements or diets)	Discontinue study treatment Discontinue study treatment Discontinue study treatment

Other concomitant medications may be considered on a case-by-case basis by the Investigator in consultation with the medical monitor.

All treatments administered to the study eye, fellow eye, and systemically must be recorded in the case report form (CRF).

10 TRIAL CONDUCT

10.1 Subject Enrollment

Before recruitment of patients into the trial, written IRB or EC approval of the protocol and informed consent must be obtained.

Enrollment into this OLE trial must be within 90 days of the patient's Month 24 visit in Study ISEE2008.

Patients who meet the eligibility criteria and have provided written informed consent will be enrolled in the trial. If any inclusion or exclusion criteria are not met, treatment with study drug should not commence. Waivers are not permitted.

10.2 Trial Assessments

Written informed consent must be obtained before any of the procedures listed below are performed. An explanation of the trial and discussion of the possible risks and discomforts will be given by the Investigator or appropriate designee. Only those patients who fulfill all eligibility criteria will be entered into the trial.

Ocular assessments performed at Month 12 and Month 18 (and at an EW visit, if performed) should be performed pre-injection (as applicable) on both eyes (OU). Ocular assessments at all other trial visits are performed only on the SE.

Screening and Day 1 (ISEE2008 Baseline) assessments were performed as part of enrollment into Study ISEE2008 (GATHER2), and therefore, are not repeated for this OLE trial. Refer to the ISEE2008 (GATHER2) protocol for Screening and Day 1 assessments and corresponding procedures (Section 10.2 and Section 7, respectively).

The following assessments, as outlined in the Study Assessments Chart (see [Section 3](#)), will be performed on the days specified below.

Note:

- **IVT injection is contraindicated in patients with active ocular or peri-ocular infections and in patients with active intraocular inflammation.**
- **Concomitant medications should be assessed at every trial visit.**
- **AEs and serious AEs (SAEs) should be assessed starting at Month 1 (first visit of this OLE trial) after the first dose of study drug until 30 days after the last dose of study drug or until the last follow up visit of the trial, whichever comes later.**

Month 1

- **Pre-Injection:**

- Informed consent (must be signed before any other assessments are performed at Month 1)
- Urine pregnancy test (if applicable)
- Immunogenicity and PK sampling
- Refraction
- BCVA (4 meters) using ETDRS chart (SE)
- LLVA
- Tonometry (SE)
- Full ophthalmologic examination (SE)
- Color fundus photography (SE)
- Fundus autofluorescence (SE)
- Optical coherence tomography (SE)
- Treatment with IVT avacincaptad pegol 2 mg

- **Post-injection:**

- Ophthalmic exam (SE) and Tonometry (SE): To ensure that the injection procedure has not endangered the health of the eye, the study eye will be assessed immediately (0 to 5 minutes) and 30 minutes after an active injection with an abbreviated ophthalmic exam. A full ophthalmic examination and tonometry will also be performed 30 minutes after injection. Assessments will continue to ensure the central retinal artery (CRA) is adequately perfused and the IOP is within 10 mmHg of the pre-injection value and stable in the opinion of the Investigator.
 - Immediately (0 to 5 minutes) post-injection:
 - Examine the gross visual function of the SE: CF, hand motion, light perception, no light perception
 - Perform direct visualization to:
 - Verify the status of the CRA: CRA is perfused and not pulsating, CRA is perfused and pulsating, CRA is pulsating, or CRA is closed.
 - Verify the retina is attached and there are no new intraocular hemorrhages.

- At 30 minutes post-injection:
 - If no CF at the previous measurement examine the gross visual function of the SE
 - Perform direct visualization to:
 - Verify the status of the CRA: CRA is perfused and not pulsating, CRA is perfused and pulsating, CRA is pulsating, or CRA is closed.
 - Verify the retina is attached and there are no new intraocular hemorrhages.
 - Perform full ophthalmic examination
 - Measure IOP
- Continue beyond 30 minutes post-injection until the CRA is adequately perfused and IOP is within 10 mmHg of the pre-injection value and is stable in the opinion of the Investigator.

Month 2 (±7 days)

- **Pre-Injection:**
 - Urine pregnancy test (if applicable)
 - Immunogenicity and PK sampling
 - Refraction
 - BCVA (4 meters) using ETDRS chart (SE)
 - Tonometry (SE)
 - Full ophthalmologic examination (SE)
 - Optical coherence tomography (SE)
 - Treatment with IVT avacincaptad pegol 2 mg
- **Post-injection:**
 - Ophthalmic exam (SE) and Tonometry (SE): Following same procedures as outlined at Month 1.

Month 3 (±7 days)

- **Pre-Injection:**
 - Urine pregnancy test (if applicable)
 - Refraction
 - BCVA (4 meters) using ETDRS chart (SE)
 - Tonometry (SE)
 - Full ophthalmologic examination (SE)

- Optical coherence tomography (SE)
- Treatment with IVT avacincaptad pegol 2 mg
- **Post-injection:**
 - Ophthalmic exam (SE) and Tonometry (SE): Following same procedures as outlined at Month 1.

Month 4 (±7 days)

- **Pre-Injection:**
 - Urine pregnancy test (if applicable)
 - Immunogenicity and PK sampling
 - Refraction
 - BCVA (4 meters) using ETDRS chart (SE)
 - Tonometry (SE)
 - Full ophthalmologic examination (SE)
 - Optical coherence tomography (SE)
 - Treatment with IVT avacincaptad pegol 2 mg
- **Post-injection:**
 - Ophthalmic exam (SE) and Tonometry (SE): Following same procedures as outlined at Month 1.

Month 5 (±7 days)

- **Pre-Injection:**
 - Urine pregnancy test (if applicable)
 - Refraction
 - BCVA (4 meters) using ETDRS chart (SE)
 - Tonometry (SE)
 - Full ophthalmologic examination (SE)
 - Optical coherence tomography (SE)
 - Treatment with IVT avacincaptad pegol 2 mg
- **Post-injection:**
 - Ophthalmic exam (SE) and Tonometry (SE): Following same procedures as outlined at Month 1.

Month 6 (±7 days)

- **Pre-Injection:**

- Urine pregnancy test (if applicable)
- Refraction
- BCVA (4 meters) using ETDRS chart (SE)
- LLVA
- Tonometry (SE)
- Full ophthalmologic examination (SE)
- Optical coherence tomography (SE)
- Color fundus photography (SE)
- Fundus autofluorescence (SE)
- Treatment with IVT avacincaptad pegol 2 mg

- **Post-injection:**

- Ophthalmic exam (SE) and Tonometry (SE): Following same procedures as outlined at Month 1.

Month 7 (±7 days)

- **Pre-Injection:**

- Urine pregnancy test (if applicable)
- Immunogenicity and PK sampling
- Refraction
- BCVA (4 meters) using ETDRS chart (SE)
- Tonometry (SE)
- Full ophthalmologic examination (SE)
- Optical coherence tomography (SE)
- Treatment with IVT avacincaptad pegol 2 mg

- **Post-injection:**

- Ophthalmic exam (SE) and Tonometry (SE): Following same procedures as outlined at Month 1.

Month 8 (±7 days)

- **Pre-Injection:**

- Urine pregnancy test (if applicable)
- Refraction

- BCVA (4 meters) using ETDRS chart (SE)
- Tonometry (SE)
- Full ophthalmologic examination (SE)
- Optical coherence tomography (SE)
- Treatment with IVT avacincaptad pegol 2 mg
- **Post-injection:**
 - Ophthalmic exam (SE) and Tonometry (SE): Following same procedures as outlined at Month 1.

Month 9 (±7 days)

- **Pre-Injection:**
 - Urine pregnancy test (if applicable)
 - Refraction
 - BCVA (4 meters) using ETDRS chart (SE)
 - Tonometry (SE)
 - Full ophthalmologic examination (SE)
 - Optical coherence tomography (SE)
 - Treatment with IVT avacincaptad pegol 2 mg
- **Post-injection:**
 - Ophthalmic exam (SE) and Tonometry (SE): Following same procedures as outlined at Month 1.

Month 10 (±7 days)

- **Pre-Injection:**
 - Urine pregnancy test (if applicable)
 - Refraction
 - BCVA (4 meters) using ETDRS chart (SE)
 - Tonometry (SE)
 - Full ophthalmologic examination (SE)
 - Optical coherence tomography (SE)
 - Treatment with IVT avacincaptad pegol 2 mg
- **Post-injection:**
 - Ophthalmic exam (SE) and Tonometry (SE): Following same procedures as outlined at Month 1.

Month 11 (±7 days)

- **Pre-Injection:**
 - Urine pregnancy test (if applicable)
 - Refraction
 - BCVA (4 meters) using ETDRS chart (SE)
 - Tonometry (SE)
 - Full ophthalmologic examination (SE)
 - Optical coherence tomography (SE)
 - Treatment with IVT avacincaptad pegol 2 mg
- **Post-injection:**
 - Ophthalmic exam (SE) and Tonometry (SE): Following same procedures as outlined at Month 1.

Month 12 (±7 days)

- **Pre-Injection:**
 - Urine pregnancy test (if applicable)
 - Refraction
 - BCVA (4 meters) using ETDRS chart (SE)
 - LLVA
 - Goldmann applanation tonometry and full ophthalmologic examination (OU)
 - Color fundus photography (OU)
 - Fluorescein angiography (OU, transit SE)
 - Optical coherence tomography (OU)
 - Fundus autofluorescence (OU)
 - Treatment with IVT avacincaptad pegol 2 mg
- **Post-injection:**
 - Ophthalmic exam (SE) and Tonometry (SE): Following same procedures as outlined at Month 1 (Note: Goldmann applanation tonometer must be used).

Month 13 (±7 days)

- **Pre-Injection:**
 - Urine pregnancy test (if applicable)
 - Immunogenicity and PK sampling
 - Refraction

- BCVA (4 meters) using ETDRS chart (SE)
- Tonometry (SE)
- Full ophthalmologic examination (SE)
- Optical coherence tomography (SE)
- Treatment with IVT avacincaptad pegol 2 mg
- **Post-injection:**
 - Ophthalmic exam (SE) and Tonometry (SE): Following same procedures as outlined at Month 1.

Month 14 (±7 days)

- **Pre-Injection:**
 - Urine pregnancy test (if applicable)
 - Refraction
 - BCVA (4 meters) using ETDRS chart (SE)
 - Tonometry (SE)
 - Full ophthalmologic examination (SE)
 - Optical coherence tomography (SE)
 - Treatment with IVT avacincaptad pegol 2 mg
- **Post-injection:**
 - Ophthalmic exam (SE) and Tonometry (SE): Following same procedures as outlined at Month 1.

Month 15 (±7 days)

- **Pre-Injection:**
 - Urine pregnancy test (if applicable)
 - Refraction
 - BCVA (4 meters) using ETDRS chart (SE)
 - Tonometry (SE)
 - Full ophthalmologic examination (SE)
 - Optical coherence tomography (SE)
 - Treatment with IVT avacincaptad pegol 2 mg
- **Post-injection:**
 - Ophthalmic exam (SE) and Tonometry (SE): Following same procedures as outlined at Month 1.

Month 16 (±7 days)

- **Pre-Injection:**

- Urine pregnancy test (if applicable)
- Refraction
- BCVA (4 meters) using ETDRS chart (SE)
- Tonometry (SE)
- Full ophthalmologic examination (SE)
- Optical coherence tomography (SE)
- Treatment with IVT avacincaptad pegol 2 mg

- **Post-injection:**

- Ophthalmic exam (SE) and Tonometry (SE): Following same procedures as outlined at Month 1.

Month 17 (±7 days)

- **Pre-Injection:**

- Urine pregnancy test (if applicable)
- Refraction
- BCVA (4 meters) using ETDRS chart (SE)
- Tonometry (SE)
- Full ophthalmologic examination (SE)
- Optical coherence tomography (SE)
- Treatment with IVT avacincaptad pegol 2 mg

- **Post-injection:**

- Ophthalmic exam (SE) and Tonometry (SE): Following same procedures as outlined at Month 1.

Month 18/End of Study (Early Withdrawal)

- Urine pregnancy test (if applicable)
- Immunogenicity and PK sampling
- Refraction

- BCVA (4 meters) using ETDRS chart (OU)
- LLVA
- Goldmann applanation tonometry (OU)
- Full ophthalmologic examination (OU)
- Color fundus photography (OU)
- Fluorescein angiography (OU, transit SE)
- Optical coherence tomography (OU)
- Fundus autofluorescence (OU)

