4.5 Exploratory Endpoint(s) Analysis

The exploratory endpoints are ophthalmic findings. All the assessments will be mapped to a scheduled visit. The mapping rule is provided in Table 2 for BCVA, OE and IOP and Table 3 for LLVA.

Best Corrected Visual Acuity (BCVA)

The score and the change from baseline of BCVA (ETDRS letters) at each analysis visit will be summarized descriptively by cohort for the FAS.

Low Luminance Visual Acuity (LLVA)

The score and the change from baseline of LLVA (ETDRS letters) at each analysis visit will be summarized descriptively by cohort for the FAS.

Low Luminance Deficits (LLD)

The score and the change from baseline of LLD (ETDRS letters) at each analysis visit will be summarized descriptively by cohort for the FAS, where LLD is calculated by the difference of BCVA and LLVA at a same visit.

Intraocular Pressure (IOP)

Baseline IOP is the pre-injection IOP value before the first study drug administration in this study.

Pre-injection IOP is defined as the last IOP value before an injection on a visit with injection (whether ACP or other treatment) or the last IOP value on a visit without an injection.

Post-injection IOP is defined as the IOP value after one injection that is closest in time to the protocol-specified post-injection timepoint (but at least 30 minutes post-injection).

Pre-injection and post-injection IOPs at each analysis visit will be summarized descriptively by cohort for the SAF with in one table. The number and percentage of participants in categories of pre-injection IOP value (≤ 21 mmHg, 22-29 mmHg, 30-34 mmHg, ≥ 35 mmHg) will be summarized at each analysis visit for each cohort.

The change from baseline of pre-injection IOPs will be summarized at each analysis visit for each cohort.

Change of IOP at each analysis visit is the difference between the post-injection and pre-injection IOPs. Change of IOP at each analysis visit will also be summarized descriptively for each cohort. The number and percentage of participants in categories of change of IOP (≤ 0 mmHg, 1-5 mmHg, 6-10 mmHg, >10 mmHg) will be summarized at each analysis visit for each cohort.

The number and percentage of participants who experienced the following events will be summarized for each cohort. The events are:

- Either pre-injection or post-injection IOP ≥ 35 mmHg,
- Had a paracentesis and
- Received IOP-lowering medications.

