4.10 Additional Conventions

4.10.1 Analysis Windows

Study Day for analysis windows will be calculated as: Date of visit/assessment – first dose of study drug in this study + 1.

The assignment of analysis visit will be consistent across all by-visit analysis datasets, and will follow the respective step-by-step algorithm:

- All assessment visits will be windowed, per the below tables, regardless of SE/FE, scheduled/unscheduled status, injection date, or pre/post-injection status.
- Baseline derivations will follow the definitions as stated in Section 4.1.

An analysis flag will be created for each record by following rules.

- **General Rules for Analysis Flags**
 - Scheduled visits falling into their respective analysis window will be prioritized over unscheduled visits.
 - If multiple observations still exist, the observation closest to the scheduled day will be selected for the analysis visit.
 - If there are two observations that have the same distance from the scheduled day, the value that is after the scheduled day will be selected for the analysis visit.
 - If more than one observation (excluding OE/IOP observation) is made on the same day, an average value for continuous measurement, or the worst value for categorical measurement, will be used for the analysis visit.
 - Any additional rules will be prespecified and documented in the TLF specifications.
- **Additional Rules for OE/IOP Analysis Flags except those in the Analysis Visit Month 18**
 - The OE/IOP records on a visit falling into its respective analysis window and with at least one SE ACP pre-injection and one SE ACP post-injection records will be firstly selected.
 - If there are no OE/IOP records satisfying the first rule, the records on a visit (whether scheduled or unscheduled) and with at least one SE ACP pre-injection and on SE ACP post-injection records will be selected.
 - If there is no OE/IOP records satisfying the above two rules, the records will be selected from a visit day (whether scheduled or unscheduled) that contain at least one pre-injection or one post-injection record to separately summarize the pre-injection and post-injection IOPs.
 - The closest OE/IOP observation to the target time will be selected for analysis.
 - If both Tonopen and Goldmann measurement are recorded available at the same time per CRF, the Goldmann measurement will be prioritized.

Listings will include all scheduled, unscheduled, and early withdrawal data.

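### The protocol gives two answers on which eyes have BCVA and LLVA measured at Month 12, and the SAP's by-visit vision summaries do not name the eye or keep same-day averaging within one eye

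*Protocol*

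**What the plan says.** **Protocol.** The opening text of Section 10.2 says that ocular assessments at Months 12 and 18, and at an early-withdrawal visit, "should be performed pre-injection (as applicable) on both eyes (OU". At every other visit it confines them to the study eye. Footnote c in Section 3 gives the same rule and is attached to the BCVA and LLVA rows of the schedule.

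The Month 12 list in Section 10.2 has "BCVA (4 meters) using ETDRS chart (SE" and an LLVA line with no eye. Two lines further on, the same list marks tonometry and the full examination for both eyes, and colour photography, angiography, OCT and autofluorescence are also marked for both eyes. The Month 18/EOS list has "BCVA (4 meters) using ETDRS chart (OU".

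**SAP.** For acuity under normal light, Section 4.5 has this sentence: "The score and the change from baseline of BCVA (ETDRS letters) at each analysis visit will be summarized descriptively by cohort for the FAS". LLVA gets a parallel sentence, also without an eye. LLD is the difference of the two at a visit, again with no eye named. By contrast, Section 4.2.3 restricts the baseline vision tables to the study eye, and the geographic atrophy area summary in 4.5 is also for the study eye.

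Section 4.10.1 sets the record handling in these words: "All assessment visits will be windowed, per the below tables, regardless of SE/FE, scheduled/unscheduled status, injection date, or pre/post-injection status". Where several observations fall on one day, continuous measurements are averaged. Only ophthalmic examination and IOP are exempt.

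**The concern.** There are two separate points.

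The first is conduct. A site that follows the Month 12 list departs from footnote c and the Section 10.2 opening text, and the reverse also holds. Month 1 is study eye only, and BCVA outside the schedule is triggered only by an ocular adverse event in the study eye (Section 3 footnote k; Section 7.1). Month 12 is therefore the only scheduled fellow-eye BCVA in this study before Month 18 or early withdrawal, and whether it exists may depend on which text a site used.

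The second is analysis. Fellow-eye acuity is collected by design at Month 18/EOS and early withdrawal, and under one reading at Month 12. The SAP does not say that the by-visit vision summaries leave it out, and its averaging rule has no within-eye condition. If programmed literally, values at the both-eye visits would describe a different quantity from values at the study-eye-only visits.

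**Working it through.** No sample size, power or alpha is involved, and the SAP tests no hypothesis. The check is a comparison of texts followed by short algebra.

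**1. Which eyes, by source**

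| Visit | Section 3 footnote c and 10.2 opening text | 10.2 list: BCVA | 10.2 list: LLVA |
|---|---|---|---|
| Month 1 | Study eye | Study eye | No eye given |
| Month 12 | Both | **Study eye** | No eye given |
| Month 18/EOS (EW) | Both | Both | No eye given |

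The only direct conflict is Month 12 BCVA. LLVA is unlabelled throughout, so the general rule is all a site has. At Month 18 every source agrees on BCVA.

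**2. The windows do not separate the eyes**

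The scheduled days reproduce:
- Month 12: 30.4375 × 11 = 334.8, rounded to 335.
- Month 18: 30.4375 × 17 = 517.4, rounded to 517.

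The windows reproduce as well:
- Table 2 (BCVA), Month 12 lower bound: 335 − (335 − 304)/2 = 319.5, rounded to 320. Month 18 lower bound: 517 − (517 − 487)/2 = 502.
- Table 3 (LLVA), Month 12 lower bound: 335 − (335 − 152)/2 = 243.5, rounded to 244. Month 18 lower bound: 517 − (517 − 335)/2 = 426.

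Table 3 has a separate window column for fellow-eye ophthalmic examination. Neither table has one for fellow-eye BCVA or LLVA. An early-withdrawal visit is measured in both eyes and placed by study day, so it can fall in an analysis visit other than Month 12 or 18.

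**3. What a literal reading would do**

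Let d be fellow-eye minus study-eye letters for one participant on one day.

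- Averaged score minus study-eye score: (SE + FE)/2 − SE = d/2.
- Change from a study-eye baseline moves by the same d/2.
- Across participants, with share f measured in both eyes and mean gap D among them, the visit mean moves by f × D/2.

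The documents give neither D nor f. Over an assumed range, the shift in letters is:

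| | D = 5 | D = 10 | D = 20 |
|---|---|---|---|
| f = 0.25 | 0.6 | 1.25 | 2.5 |
| f = 0.5 | 1.25 | 2.5 | 5 |
| f = 1 | 2.5 | 5 | 10 |

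**4. LLD at Month 12**

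Suppose a site takes BCVA from the list (study eye) and LLVA from the general rule (both eyes). Under literal averaging, LLD would be the study-eye BCVA minus a two-eye LLVA mean. It would be off by minus half the between-eye LLVA difference. This too depends on the literal reading.

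**The case against.** The best case for the plan is that eye-mixing is a strained reading. Windowing without regard to eye only assigns a visit label; it does not pool eyes. A same-day average naturally means repeats of one measurement, and nowhere does the SAP say that right-eye and left-eye acuity are combined into one score. The baseline vision tables are for the study eye. Table 3 treats fellow-eye examination as its own series. Where the SAP uses fellow-eye data, as in ocular history, lens status and ocular adverse events, it names the eye. SAP 4.6 also says that a fellow eye treated with study drug is not a second study eye, although that sentence sits in the safety section and does not address averaging. Table formats and further selection rules are deferred to TLF specifications, which are not among the documents and may restrict these tables to the study eye. Most of this stands, and it makes a study-eye analysis the likely intent. It does not change the wording, which leaves that intent unstated for BCVA, LLVA and LLD.

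On the protocol side, no planned analysis uses fellow-eye vision. The fellow-eye tables after treatment with study drug or Syfovre are adverse-event tables, and the special-interest event of a 30-letter BCVA loss is confined to the study eye. This stands too. It limits the consequence but leaves the contradiction in current text.

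A reader might infer more than the documents support:
- **That fellow-eye BCVA is missing at some sites.** The texts show only that sites could differ, and only for Month 12.
- **That a false step will appear at Months 12 and 18.** That needs literal programming and a non-zero mean gap, and neither is shown.
- **That the Month 12 line deprives the fellow eye of a baseline.** Month 1 is study eye only under the general rule, so settling Month 12 either way creates no baseline.

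**Conclusion.** The point holds in two parts and is minor.

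The protocol contradicts itself on Month 12 BCVA and leaves LLVA unlabelled. Sites may collect different data, and one of the two scheduled fellow-eye BCVA measurements may be absent.

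SAP 4.5 does not name the eye for the by-visit BCVA, LLVA and LLD summaries, and the averaging rule in 4.10.1 is not limited to one eye. Applied literally, it would move a participant's value by half the between-eye difference, for example 5 letters at an assumed 10 and 10 letters at an assumed 20. These are illustrations per participant, not estimates of bias in any reported mean. The risk is conditional on literal programming and on TLF specifications that do not already restrict the tables to the study eye.

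Severity is low because BCVA and LLVA are exploratory, LLD is derived from them, everything is descriptive, and the primary adverse-event endpoint does not rest on these summaries.

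**What to change.** 1. **Protocol:** reconcile the Month 12 eye designation for BCVA and LLVA between Section 3 footnote c, the opening text of Section 10.2 and the Month 12 list, so that one rule applies at every site.
2. **SAP 4.5:** add *of SE* to the BCVA, LLVA and LLD summaries, as is already done for geographic atrophy area.
3. **SAP 4.10.1:** limit same-day averaging to records of the same eye.

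Separate fellow-eye rows at Months 12 and 18 are optional. They would be an additional summary, not the repair of an error.

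The cost is a correction to the Month 12 list or to the general rule, plus a few words in two SAP sections. No visit is added. The SAP edits need no new data and are worth making before database lock, even if Month 12 visits have already taken place.
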